4.5. Will this research be conducted by SU investigators in foreign countries?

No. (Skip to 4.6)
 Yes. An International Research Form must be completed and submitted with this application.
<http://researchintegrity.syr.edu/wp-content/uploads/2016/10/International-Research-Form-2013.doc>

4.6. Will this research involve genetic testing?

No. (Skip to Section 5)
 Yes. A Genetic Research Form must be completed and submitted with this application.
<http://researchintegrity.syr.edu/wp-content/uploads/2016/10/Genetics.doc>

5. Performance Site Information

5.1. Describe how you will have adequate facilities to conduct your study.

The Speech Production Laboratory (PI, [name]) at [name] was designed for clinical data collection from children. [name] has been running studies with children for 3 years. He currently has the equipment required (ultrasound, recording devices, testing materials, etc.) to conduct this project.

5.2. List all Performance Sites Other than SU (insert additional rows if needed).

(This may apply when a SU investigator collaborates with a non-SU investigator or institution. Please check all that apply and add additional sites. Each will require a letter of cooperation and/or IRB approval.)

Check all that apply	Name of Performance Site (list all participating sites below)	IRB Approval and/or Letter of Cooperation
	SUNY Upstate Medical University	 Attached  Pending
	*Syracuse City Schools	 Attached  Pending
	*Other, specify site:	 Attached  Pending

*The following additional information is required: contact information for the site, if the site has an IRB, and whether the IRB has approved the research, or plans to defer review to SU's IRB:

5.3. Will this research be conducted in a school or is it funded by the US Department of Education?

No (Skip to 5.4)

Yes. If yes, complete the form found at:

<http://researchintegrity.syr.edu/wp-content/uploads/2016/10/Department-of-Education-Schools-Form.doc>

5.4. Is this a multi-center research project in which Syracuse University will function as the coordinating center/lead institution? (A multi-center study is one where different PIs at different institutions are conducting the same study.)

No

Yes. If yes, describe the plans to manage information obtained in multi-site research that may be relevant to the protection of research participants such as: unanticipated problems involving risks to participants or others, interim results, and protocol modifications:

6. Research Qualifications

A manual has been developed outlining the protocols that are to be followed. All members of the team will be required to read the manual to ensure familiarity with technical and procedural issues. We will hold weekly lab meetings to review both procedural/compliance issues as well as scientific issues. We will outline responsibilities at each meeting (currently using the web-based system ASANA) and we will keep a running log of the status of recruitment, participation, data collection, data safety/confidentiality, and data analysis. All members are CITI-certified and will be instructed to immediately bring to the PI's attention any Human Subjects related issues.

6.5. Explain how you will have adequate numbers of qualified staff to conduct your study.

The staff listed above are sufficient to collect and manage data from approximately 15 children per year and to conduct data management/coding activities for those participants.

7. Characteristics of Participants

7.1. Approximate Number of Participants to be recruited: 40

7.2. Sex: M F Both

7.3. Age Range-Check all that apply:

0-6 (Include parental consent form)
 7-17 (Include parental consent form and child assent form)
 18-64
 65 and older

Exact ages to be included: 9;0 – 17;11

7.4. When the age range indicates an upper limit, provide justification: This age range is chosen as it is sufficiently restrictive to enable homogeneity of participants, with all participants beyond the age of typical acquisition of speech sounds (approximately age 8-9 yrs, Smit et al., 1990); additionally, prior work has shown that children below the age of 8 may show less growth with biofeedback treatments (Sjolie et al., 2016). Because participants may be randomized to a treatment condition with an intensive component (e.g., 10 hours of therapy over 5 consecutive days), participants need to be old enough to maintain attention to cognitively demanding tasks over long durations.

7.5. Does this study target one gender or specific social/ethnic group(s)?

No. (Skip to 7.6)
 Yes. If yes, answer 7.5.1. and 7.5.2. below.

7.5.1. If yes, check all that are targeted/vulnerable populations (Code of Federal Regulations: http://www.access.gpo.gov/nara/cfr/waisidx_00/45cfr46_00.html).

*These additional forms can be found on the IRB Website under Special Populations:

<http://researchintegrity.syr.edu/human-research/forms/>

Children/minors - *Requires additional form*
 Cognitively impaired - *Requires additional form*

- Prisoners** - * Requires additional form*
- Pregnant women** - *Requires additional form*
- Legally restricted, non-prisoner**
- Educationally disadvantaged**
- Economically disadvantaged**
- Elderly/aged**
- Other, specify:**

***NOTE*:** These additional forms can be found on the IRB Website (under Special Populations):

<http://researchintegrity.syr.edu/human-research/forms/>

7.5.2. Explain the rationale for using this particular group(s): This is the age at which most children have typically acquired speech sounds; therefore, any errors present are unlikely to resolve due to maturation effects. Also, children over the age of 9;0 are more likely to sustain attention during tasks which are cognitively demanding.

7.6. List the inclusion criteria:

Participants must be native English speakers who hear English as the dominant language in their home setting. Participants must be in the age range of 9;0 – 17;11. In the initial evaluation, all participants must pass a hearing screening. Additionally, participants must score at or better than -1.3 standard deviations from the mean on the Matrix Reasoning Task of the Wechsler Abbreviated Scale of Intelligence – 2nd Edition (WASI-2; t-score \geq 37), Peabody Picture Vocabulary Test – 4th Edition (PPVT-4; standard score \geq 80), and the Following Directions subtest of the Clinical Evaluation of Language Fundamentals – 5th Edition (CELF-5; scaled score \geq 6). Speech sound errors will be confirmed by the administration of the Goldman-Fristoe Test of Articulation – 3rd Edition (GFTA-2; percentile \leq 5th). A diagnosis of CAS will be verified using three research supported tasks which assess the participant's the ability to plan/program complex speech movements. The 3 primary tasks described below, which have been part of our assessment battery to date, have been independently developed in previous studies in Sydney, AU, Nijmegen, NL, and Madison, WI. Based on published procedures, we will require that participants meet CAS diagnostic criteria on at least 2 of the 3 tasks described below.

Task	Description	Measures	Published Sensitivity/ Specificity
Polysyllable task (Murray, McCabe, Heard, et al., 2015)	Naming of 80 polysyllabic words (e.g., kangaroo)	Percent Consonants Correct, Percent of words with appropriate lexical stress, Percent syllable transitions with segregation.	97% / 100% (when combined in a model with DDK task below, Murray et al., 2015)
Diadochokinetic task (Thoonen et al., 1999)	Rapid sequences of /pʌtʌkʌ/	Rate and accuracy of tri-syllables	100% / 91 %
Syllable Repetition Task (Shriberg et al., 2009; Shriberg et al., 2012)	Participant repeats nonsense words of 2-4 syllables (e.g., /bamadana/)	Number of items (out of 18) with phoneme additions	74.6% / 93.4%

7.7. List the exclusion criteria:

Participants will be excluded if parent report or direct evaluation reveals oral-facial structural abnormalities (e.g., cleft palate). We will not study participants whose parents report known genetic syndrome, neurobehavioral disorders (e.g., autism spectrum disorders, ADHD, obsessive-compulsive

disorder), or vision problems that are corrected with glasses/contacts.). We will also exclude individuals who fail a hearing screening during the eligibility visit. These restrictions are put into place to enhance the internal validity of the study. In order to avoid confounding interpretation of the relations between treatment outcomes and language or cognitive abilities, we will exclude individuals with low nonverbal abilities (as identified as being below the inclusionary criteria on the Matrix Reasoning subtest of the WASI-2, PPVT-4, or Following Directions Subtest of the CELF-5). Participants will also be excluded if they do not meet the CAS diagnostic criteria on 2/3 of the tasks described above. A Dysarthria Score of 2 on the Maximum Performance Tasks is also considered exclusionary (to avoid confounding interpretation of treatment outcomes). Participants who are not in the target age range during the entire range of their participation (9;0 – 17;11) will also be excluded.

7.8. Does this research involve participants likely to be vulnerable to coercion or undue influence?

No. (Skip to 7.9)
 Yes. If yes, describe the additional protections included in the protocol to protect their rights and welfare.

7.9. General state of Health: ("Unknown"- *unless you will obtain health data on participants prior to beginning the study.*)

"[Suspected] childhood apraxia of speech" The clinical diagnosis is inconsistently applied; therefore, we will use our own criteria to make this determination.

8. Recruitment of Participants

8.1. Describe in detail how participants will be identified and recruited. Include in your description how you will have access to a population that will allow recruitment for the number of participants required for your research. Do not merely state "Volunteers".

Participants will be identified and recruited through flyers, informational letters, and emails that will be distributed to local speech-language pathologists who will be invited to share information about the study with parents of children who might benefit from participation in the study. In addition, flyers and online postings will be used to reach out to parents in the surrounding communities. Online postings will consist of a link to the flyer available via the (1) CSD department website (csd.syr.edu); (2) Speech Production Lab Website (speechproductionlab.syr.edu); (3) SU Today; (4) the American Speech-Language Hearing Association's CLARC program (Clinicians and Researchers Acting Together; community.asha.org/clarc) of which [name] is a member; and (5) the Childhood Apraxia of Speech Association of North America (CASANA.org). The research team will also contact the Gebbie Clinic ([name]), and private speech-language clinics (with publicly available addresses) and invite personnel at these locations to post/share a copy of our flyer; they are free to decline. An announcement will be placed in the SU CSD Alumni newsletter and flyers will be passed out at Continuing Education events for speech-language pathologists throughout the year. We will pay to put an ad in the Central New York Speech-Language Hearing Association newsletter. Additionally, links to information on the website will be tweeted ([name], [name], @SyracuseCSD) and posted to Facebook ([name] page, CNYSLHA page).

Additionally, we will coordinate with speech-language pathologists at various schools. Letters of support are attached.

8.2. Describe who will recruit participants.

[name], [name], [name]

8.3. Identify all applicable recruitment methods that apply: NOTE:Copies of all advertising materials including flyers, posters, ads, letters, scripts or detailed descriptions; including graphics **MUST** be provided with your application. (See SOP 036 for Recruitment/Advertising).

 Flyers	 Mass E-mail Solicitation	 SU Today News Service
 Internet	 Posters	 Television
 Letter	 Newspaper	 Departmental Research Boards
 Telephone	 Radio	 Social Media
 Other (describe):		
 Not applicable		

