11. Three Individual Phrase Probe Lists. ~5 minutes each, 15 minutes total. Based on speech sound errors observed in Baseline 1, specific error patterns will be identified. Individual probes addressing an error pattern will be administered. Participants will read a list of 20 phrases containing the target pattern (e.g., for onset /l/ examples might be: “please go left” and “light the flame”). Percent accuracy will be collected on number of target sounds produced correctly out of 40 using a binary scoring system (i.e., incorrect = 0; correct = 1).

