Aim 1: In addition to the above assessment visits, participants will be randomized to one of four treatment conditions.

Table 1: Four groups to which children will be randomized in a 2 x 2 Factorial design

Distribution Conditions	Biofeedback Conditions	
	Sequenced Biofeedback (Biofeedback → No biofeedback)	No biofeedback
Sequenced Distribution (massed→distributed)	n=10	n=10
Distributed Practice	n=10	n=10

We will randomize children with CAS to one of four groups. We will test generalization effects in a x 2 (Mass→Distributed vs. Distributed only Practice Schedule) x 2 (Sequenced Biofeedback→No biofeedback vs. No biofeedback) factorial treatment design.

Participants will be randomly assigned to either Distributed Practice or Sequenced Distribution (massed→distributed practice). In both conditions, the cumulative treatment dose will be 20 hours of treatment. Half of our participants (n=20) will receive treatment following a distributed model of twice per week for 60 minutes for 10 weeks, for a total of 20 hrs of therapy. The remaining participants (n=20) will receive treatment following a sequenced approach of massed then distributed practice, with 10 hrs occurring in the first week (2 hrs per day for 5 days, with a 10 minute break in between sessions each day), then 3 one-hour sessions per week for 2 weeks, and finally 2 one-hour sessions per week for 2 weeks.

Table 2: Overview of Aim 1 Schedule by Group: Operationalized Definitions

	Wk 1	Wk 2	Wk 3	Wk 4	Wk 5	Wk 6	Wk 7	Wk 8	Wk 9	Wk 10	Wk 15
Distributed Practice Group (n=20)	1 hr x 2 visits & Assess	1 hr x 2 visits & Assess	Assess								
Sequenced Distribution Group (n=20)	2 hr x 5 visits	1 hr x 3 visits	1 hr x 3 visits	1 hr x 2 visits	1 hr x 2 visits & Assess	-	-	-	-	Assess	Assess

Aim 2: In addition to the above randomization based on schedule, half of the participants (n=20) will be randomized to receive treatment without ultrasound visual feedback and half (n=20) will be randomized to receive treated with ultrasound. The practice structure described above (see *Overview of Treatment Procedures*) will be identical, and the difference between conditions therefore will be whether or not the clinician and client have access to a visual referent during speech production to describe aspects of both erred and correct tongue movements.

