In the Sequenced Biofeedback → No biofeedback condition, participants begin treatment such that ~50% of the session includes ultrasound feedback of the tongue. Each session will be divided into four 13 minute Time Periods (A, B, C, D). The ultrasound will be available for practice in Time Periods A and C, whereas practice will continue without ultrasound for periods B and D. When the ultrasound is used in Time Periods A and C, it will be available only when the participant is practicing at treatment Levels 1 (syllables), 2 (monosyllabic words), 3 (multisyllabic words) and 4 (phrases). However, after 8 hrs of treatment, *ultrasound use will be faded* such that it is only available as children are at practice Levels 1 and 2 to encourage independent practice without visual support at more complex levels. During the final 4 hours of treatment, no visual feedback will be available.

[figure not shown]
Table 3: Structure for a 60-min Session: Operationalized Comparison of Ultrasound use for Aim 2

Sequenced Biofeedback → No Biofeedback Group (n=20)				
Time Period:	A	B	C	D
Treatment target	Target 1	Target 1	Target 2	Target 2
Ultrasound available: First 8 hrs of therapy	Used on Levels 1: Syllables 2: Monosyllabic words 3: Multisyllabic words 4: Phrases	None	Used on Levels 1: Syllables 2: Monosyllabic words 3: Multisyllabic words 4: Phrases	None
Next 8 hrs of therapy	Used on Levels 1: Syllables 2: Monosyllabic words	None	Used on Levels 1: Syllables, 2: Monosyllabic words	None
Last 4 hrs of therapy	None	None	None	None
No Biofeedback Group (n=20)				
Time Period:	A	B	C	D
Treatment target	Target 1	Target 1	Target 2	Target 2
Ultrasound use	None	None	None	None

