When biofeedback is required, we will use an EchoBlaster 128 ultrasound with PV 6.5 probe to provide real-time visual display of the tongue. When it is available, *all verbal feedback* by the clinician will be expected to reference the visual display. For example, when treating /-ks/ sequences, feedback can be provided to the client about elevation of the tongue body and lowering of the tongue tip for /k/, followed by elevation of the tongue tip/blade for /s/. The participant's attention will therefore be drawn to these movements on the screen and participants will be instructed to visually monitor their speech movements and make corrections based on the visual feedback. As an example, **Figure 2** shows ultrasound images for /r/ (anterior is right, posterior left). The distorted /r/ (top) has a low tongue tip/blade (right side of the image) and high tongue body, whereas the correct /r/ (bottom) has a high tongue tip/blade and a lowered tongue body.

When no biofeedback is required, practice will be similar to traditional speech therapy.

Feedback will be based on the clinician's percept of the child's production unaided by technology. However, the practice and feedback structure will still follow that which is outlined in Table 3.

Overview of Treatment Session Procedures

A manual is posted on our website outlining practice procedures (speechproductionlab.syr.edu). The general structure involves a pre-practice stage and a practice stage in each session. During **pre-practice**, target sound sequences (e.g., /lo-/) are elicited through frequent phonetic cues, shaping strategies, and verbal descriptions of articulation. When biofeedback is available, and visualization of is used to encourage the child to modify shape and position and to properly sequence movements for acceptable productions. A pre-established criterion (i.e., 12 correct productions of the target) must be met to progress from the pre-practice stage to the practice stage. For clients with significant difficulty producing the target sound sequences, pre-practice may take the majority of a session (during the early stages of therapy); for clients who have developed the ability to successfully perform the task (during the later stages of therapy), pre-practice may be completed in 1-2 minutes.

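### As written, the vision criterion excludes children whose vision is corrected and sets no exclusion for uncorrected problems; the sponsor should confirm which rule is meant

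*Protocol*

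**What the plan says.** Protocol Section 7.7 (exclusion criteria) opens its list with "We will not study participants whose parents report known genetic syndrome, neurobehavioral disorders" and closes the same sentence with "vision problems that are corrected with glasses/contacts". The vision clause is therefore an exclusion, and it rests on parent report. A little further on, the section gives one reason for its restrictions as a group: they are meant to strengthen internal validity. It gives no reason specific to vision.

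Two parts of the trial depend on sight:

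- **The ultrasound condition.** Under Aim 2 in Section 4.1, "half (n=20) will be randomized to receive treated with ultrasound". When the display is on, "participants will be instructed to visually monitor their speech movements and make corrections based on the visual feedback".
- **The phrase probes, in every group.** At Baseline 2 and at each progress assessment, "Participants will read a list of 20 phrases containing the target pattern", for each of three lists. The SAP takes its dependent variable, percent target sounds correct, from phrase probes.

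**The concern.** An exclusion meant to protect internal validity would be expected to remove children who cannot see the materials well. This one removes children whose sight has been put right and is silent about those whose sight has not.

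Three things are at stake:

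- **Who is turned away.** Staff who follow the text refuse children who wear glasses or contact lenses and could do every task.
- **Who is let in.** The text gives no ground to exclude a child with a reported, uncorrected problem.
- **What the protocol describes.** If staff silently read in a 'not', the enrolled population is no longer the one the protocol defines, and a reader cannot tell which rule was used.

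**Working it through.** The documents state no figure tied to this criterion, so the check is a reading of the text.

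**1. The sense of the clause.** The governing verb is that the study will not enrol such participants. The items under it are genetic syndromes, neurobehavioral disorders (with examples in brackets) and vision problems. Nothing in the sentence reverses the sense for the last item. A stray full stop and bracket after the vision clause show loose editing but do not change the meaning.

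**2. What each version of the rule does.**

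| Vision status reported by parent | Rule as written | Rule with 'not' restored |
|---|---|---|
| No problem | not excluded | not excluded |
| Problem, corrected | excluded | not excluded |
| Problem, not corrected | not excluded | excluded |
| Problem the parent does not know of | not excluded | not excluded |

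The two versions give opposite answers in the second and third rows and agree in the other two.

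**3. Whether another passage supplies the missing rule.** The inclusion criteria (Section 7.6) do not mention vision. Evaluation Visit 1 screens hearing and lists no vision screen. The SAP does not address eligibility. Section 9.6 mentions a phone screening, but the form is not among the documents and its content is unknown. Section 7.7 is therefore the only vision rule available.

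**4. Whether the literal rule serves the stated purpose.** Children allocated to ultrasound must use a screen image to correct their speech, and all 40 planned children read the probes. An uncorrected problem could interfere with both tasks; a corrected one should not. Removing the second and keeping the first does not serve internal validity.

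**5. How far other eligibility steps cover the gap.** Visit 1 includes three picture-based tests with minimum scores: Matrix Reasoning (T-score 37), PPVT-4 (standard score 80) and Following Directions (scaled score 6). A child who could not see the pictures would probably fall below a cut-off. The articulation test and the polysyllabic naming task also use pictures. None of these requires reading text. Randomisation follows Visit 1, and the probes are first read at Baseline 2, where they are not an eligibility criterion. The tests would stop the more severe problems. Whether they would stop milder ones cannot be told.

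**6. Size.** The documents give no number or share of children with corrected or uncorrected vision. No effect on recruitment, or on the planned 40, can be computed from them.

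**The case against.** **It is only a drafting slip, and the protocol has others.** Test editions are mislabelled in places and some sentences lack words. That is true, and a slip is the likeliest explanation. But this one sits in operative eligibility text and reverses who may enrol, so it deserves correction rather than tolerance.

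**The word may have been lost when the PDF was read.** This cannot be ruled out from the text. It is why the sponsor should check the source document before changing anything. If the source already contains 'not', the point falls away.

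**A reason is given.** This stands in part. Section 7.7 offers internal validity as a general reason for its restrictions, so it would be wrong to say that the exclusion is unexplained. What is missing is a reason specific to corrected vision, and the general one does not fit the literal rule.

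**The visual tests at Visit 1 already protect the trial.** This also stands in part. They would stop the more severe problems, and the documents do not show that any child would pass them and yet be unable to read a phrase list or see the display. They do nothing for the children with corrected vision who are turned away.

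**A stronger reading is tempting:** that the wording weakens the ultrasound comparison, or that its harm can be gauged from how much display time and reading the trial involves. The documents support neither. The criterion applies before randomisation and equally to all groups, so it does not bias the comparison, and nothing shows a diluted effect. Display time and reading load would be the same with the 'not' restored, so they do not measure the consequence of the wording.

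**Conclusion.** The point holds as a defect in the eligibility text. Followed literally, Section 7.7 turns away children who see well with correction and does not exclude reported uncorrected problems. That does not serve the purpose the section states for its restrictions.

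The consequence is for who is enrolled and to whom the result applies. No alpha, power or sample-size figure changes, and the size of the effect on enrolment is unknown.

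The conclusion rests on the extracted wording being faithful to the source. That a 'not' was dropped is a further inference, probable but unconfirmed. The correction should be made because it costs almost nothing and the present text may say the opposite of what is meant.

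**What to change.** Check Section 7.7 against the source document and confirm the intended rule.

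- **If 'not' was dropped:** reword so that the exclusion covers vision problems that are not corrected by glasses or contact lenses, still by parent report. This will not find problems the parent does not know of. Make any screening or eligibility form that carries the criterion match.
- **If the literal rule was intended:** state the vision-specific reason, and describe the study population as children without corrected vision.
- **If enrolment has begun:** report which rule was applied in practice and how many children it excluded. The SAP is written partly in the past tense, so this may already be the case.

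The cost is one word in the protocol if the inference is right, plus a check of any form that carries the criterion. The visit schedule and the analysis do not change.
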